“Effects of dapagliflozin on blood pressure variability in patients with prediabetes and prehypertension without pharmacological treatment: a randomized”

NCT03006471

June 9, 2016

Introduction

There is a reciprocal relationship between the possibilities of developing arterial hypertension (HT) and diabetes mellitus type 2 (DM2). The probability of developing HT in patients with DM2 is 40% in the first 5 years of diagnosis and 12% in the development of DM2 in HT. The prevention or timely detection of these conditions can reduce the risk of the development of cardiovascular disease (1).

Prediabetes and prehypertension are defined as metabolic states that lead to the appearance of DM2 and HT, respectively.

Approximately 12 million people suffer from prediabetes in Mexico according to the report of the International Diabetes Federation (IDF) in 2017 (2). In 2015, a global prehypertension prevalence of 37.5% will be reported according to the 8th report by the Joint National Committee (JNC8) (3).

Ambulatory blood pressure monitoring (ABPM) is superior to office BP to predict cardiovascular mortality and its most potent component is the alteration in nighttime blood pressure variability (BPV) compared to daytime (4).

Sodium-glucose cotransporter inhibitors type 2 (iSGLT-2) are oral antidiabetics that improve glycemic control. Dapagliflozin promotes natriuresis and osmotic diuresis, which decreases plasma volume and decreases blood pressure (BP) in patients with DM2; however, until now it is unknown whether this effect could modify BPV in individuals with prediabetes and prehypertension without pharmacological treatment (5,6).

Methods

A clinical study, double-blind, randomized and placebo control group in 30 patients. Men and women (30-60 years) diagnosed with prediabetes according criteria of the American Diabetes Association (ADA) with fasting plasma glucose (FPG) 5.6-6.9 mmol/L (>2 occasions) or the 2 h plasma glucose (2-h PG) value during a 75-g oral glucose tolerance test 7.8-11.0 mmol/L, or both (7) and prehypertension according criteria of the JNC8 with BP of 120-139 / 80-89 mmHg (3).

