The FPG and 2-h PG (mmol/l) will be quantified from the serum obtained from a 5 ml sample of venous blood centrifuged at 2500 rpm and the amount of glucose will be determined by colorimetric methods with the automatic clinical chemistry analyzer Erba XL 100™ (Mannheim, Germany), and with an intra- and inter-assay coefficient of variability of < 1% and 2%, respectively. The hemoglobin glycosylated A1c fraction (A1C) (%) will be measured using high-performance liquid chromatography (HPLC) (Bio-Rad Laboratories, Hercules, CA, USA) with an intra- and inter-assay coefficient of variability of 0.4% and 1.6%, respectively.

ABPM will be recorded during 24 h using an oscillometric method with the Microlife WatchBP O3 (Microlife AG, Widnau, Switzerland). BP measurement will be scheduled every 15 minutes during the day (8 a.m. to 11 p.m.) and every 30 minutes during the night (11 p.m. to 8 a.m. of the next day) (8). Patients will be instructed to continue with the usual activities during the ABPM and they will be advised to remain calm when they felt the pressure increase in the cuff. The

method will be considered reliable if more than 70% of valid measurements will be met.

The BPV will be calculated: 24-h BP; daytime and nighttime BP; BP weighted standard deviation (SD) (the average of the daytime and nighttime BP SD each weighted for the duration of the respective day or night period), this method has been proposed as a method of excluding day to night BP changes from the quantification of overall 24 h SD, without discarding either daytime or nighttime values; the coefficient of variation (CV) of 24-h, daytime and nighttime (the average SD of SBP divided by the corresponding mean BP and multiplied by 100); the mean real variability (AVR) of SBP and DBP (the average of the absolute differences between consecutive BP measurements); and identify the dipper circadian BP pattern (BP nightly decline between 10-20% of the BP day, this is normal), Non-dipper (night decrease in BP <20% compared to the BP of the day), dipper reverse (increase in night-time BP compared to day BP), dipper extreme (BP nightly decline between >20% of the BP day) which are relevant to cardiovascular prognosis (9).

Also, will be identified through the ABPM by 24-h: mean arterial pressure (MAP), daytime and nocturnal hypertensive load.

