Adherence to treatment and the presence of adverse events will be assessed with an attachment diary that will be given to the patient at study entry, as well as a record of medications and returned by patients at each visit.

The formula for clinical trials will be used to determine the sample size (10), with a statistical confidence of 95% and a power of 80%, as well as the SD and the expected difference for each of the primary variables (11), a total of 8 and 12

patients will be obtained for the SBP and the DBP, respectively. The highest n obtained will be taken into account, to which 20% will be added for possible losses. A total of the 15 patients per group will be estimated in this calculation.

Analysis

Data will be analyzed with the software IBM SPSS Statistics V21.0 software (SPSS, Inc., Chicago, IL, USA)..

The Mann-Whitney U test (non-parametric test for quantitative variables) is used to evaluate the differences between the intervention groups expressed in means and SD; Wilcoxon (non-parametric test for quantitative variables) will be used to evaluate the differences between the baseline and final evaluation of each group expressed in means and SD; and Pearson's Chi2 or Fisher's exact test (non-parametric test for qualitative variables) will be used to evaluate the differences between the intervention groups expressed in frequencies and percentages.

A $p \leq 0.05$ is considered statistically significant.

The present study will be consistent with the Helsinki declaration and will be approved by the Local Committee of Ethics and Research of the University with this register number CEI/357/2016 and Clinical Trials NCT03006471. The informed consent will be obtained from the participants before performing any intervention or evaluation. The principal investigator explained to each participant the nature, risks and benefits of the study.

Financing

The financing will be with own resources by the University of Guadalajara.

References

1. International Diabetes Federation. Atlas de la diabetes de la FID. 2015 [updated in 2015]. Available from: https://www.fundaciondiabetes.org/upload/publicaciones_ficheros/95/IDF_Atlas_2015_SP_WEB_oct2016.pdf.

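### Dipping pattern is left to an unordered class test with overlapping boundaries; the percentage nocturnal fall should be prespecified as a continuous outcome

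*Combined protocol and SAP*

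**What the plan says.** The ABPM paragraphs in Methods list daytime and nighttime BP and several variability indices. They then say the recording will be used to "identify the dipper circadian BP pattern" and the three other patterns. The boundaries are all expressed as the night fall relative to daytime BP:

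- dipper: 10-20%
- non-dipper: below 20%
- reverse: a rise at night
- extreme: above 20%

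The text does not say whether systolic or diastolic pressure defines the class. It does not list the percentage fall as a variable to be analysed.

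The Analysis section works by type of variable. Quantitative variables go to Mann-Whitney between arms and Wilcoxon within arms. Qualitative variables go to "Pearson's Chi2 or Fisher's exact test" between arms. Neither dipping nor a four-class table is named, and no ordinal test or baseline adjustment appears anywhere.

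The sample size rests on "the SD and the expected difference for each of the primary variables", namely SBP and DBP. It gives "a total of 8 and 12" patients, "to which 20% will be added for possible losses", hence 15 per group.

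**The concern.** Each patient's percentage fall has to be worked out in order to assign a class. If only the class is then compared, by a test that treats the four classes as unordered labels, three things are discarded: the order of the classes, the size of the fall, and the patient's baseline value. With 15 patients per arm or fewer there is little information to spare, and a real shift in the night-to-day pattern could go undetected for avoidable reasons.

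The overlap of the boundaries is a separate fault that depends on no assumption. Two analysts following the text could place the same patient in different classes and so obtain different tables and p-values. The continuous fall needs no cut-points.

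**Working it through.** **1. The plan's own figure.** Base n is 12 (DBP), read as per group, with 20% for losses: 12/(1 - 0.20) = 15, or 12 × 1.2 = 14.4, rounded up to 15. The stated 15 per group is reproduced. After 20% losses, 15 × 0.8 = 12 remain, hence the range of 12 to 15 per arm.

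**2. The effect implied by that n.** No difference or SD is stated. Inverting n = 2(z₀.₉₇₅ + z₀.₈₀)²/d², with two-sided 5% assumed because sidedness is not stated, d = √(2 × 7.85/12) = 1.14 for n = 12 and √(2 × 7.85/8) = 1.40 for n = 8. These apply to SBP and DBP, not to dipping, and serve only as a yardstick.

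**3. The classes.** A fall of 15% satisfies 10-20% (dipper) and also satisfies below 20% (non-dipper). Every dipper short of exactly 20% meets both definitions.

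**4. Power.** All inputs for the fall are assumptions: normal distribution, control mean 8-10%, SD 6-7 points in both arms, baseline-final correlation 0.4, and a pure shift in one arm. Cuts at 0, 10 and 20% were used only so that a table could be formed. The class test is the exact Fisher (Freeman-Halton) test on the 2×4 table at the final visit. A 5-point shift is 5/7 to 5/6 = 0.71 to 0.83 SD; a 7-point shift is 7/7 to 7/6 = 1.00 to 1.17 SD. Simulated power with 15 per arm:

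| Shift | Fisher, four classes | Mann-Whitney on the fall | ANCOVA on the fall |
|---|---|---|---|
| 5 points | 24-32% | 45-56% | 53-65% |
| 7 points | 46-61% | 70-85% | 80-92% |

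Repeat runs move the ends of these ranges by a few points.

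**5. Loss due to the classes alone.** Mann-Whitney is the like-for-like comparator: it is the plan's own test for quantitative variables and uses no baseline. Setting like ends of the ranges together, the loss is 1 - 24/45 = 47% and 1 - 32/56 = 43% at 5 points, and 1 - 46/70 = 34% and 1 - 61/85 = 28% at 7 points. A wider set of assumptions (control mean 5-12%, SD 5-8 points) gives the share of Mann-Whitney power that Fisher keeps:

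| Effect | 12 per arm | 15 per arm |
|---|---|---|
| 0.5-0.8 SD | 0.44-0.58 | 0.49-0.61 |
| 1.15 SD | 0.57-0.65 | 0.66-0.74 |
| 1.4 SD | 0.68-0.76 | 0.78-0.84 |

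At 1.14 SD the four-class test needs about 22-24 per arm for 80% power, against 15 or fewer for Mann-Whitney.

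**6. Which of the two named tests.** With 12 to 15 per arm, at least one non-empty class had an expected count below 5 in 89-100% of simulated tables, so Pearson's test would rarely be suitable. Fisher is valid but conservative: its type I error was 2.8-4.3% under the step 4 assumptions.

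**7. Baseline adjustment.** At correlation 0.4, ANCOVA multiplies the residual SD by √(1 - 0.4²) = 0.92. A simple change from baseline multiplies it by √(2(1 - 0.4)) = 1.10. Adjustment therefore helps at this correlation, while subtracting the baseline costs a little.

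**The case against.** The case against has several sound parts.

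- **The four-class test is inferred.** The plan says only that the pattern is identified. Nothing rules out a Mann-Whitney test on the fall. This stands, but nothing specifies that test either, and adding it after unblinding would be post hoc.
- **Night pressure is already analysed as a continuous variable.** Daytime and nighttime BP each go to Mann-Whitney. This stands in part: two separate tests of level do not test the relative fall, which is what the classes describe.
- **Fisher's test is valid in small samples.** True. The issue is the information discarded, not validity.
- **ANCOVA against Fisher is not like for like.** Correct. At a 5-point shift, 53 - 45 = 8 to 65 - 56 = 9 points of the gap come from the step from Mann-Whitney to ANCOVA, not from the classes.
- **The sample is small whatever the method.** At a 5-point shift even ANCOVA reaches only 53-65%.

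Two stronger readings are tempting. A reader might infer that the plan itself ranks dipping as the most prognostic measure, from the Introduction's remark on ABPM that "its most potent component is the alteration in nighttime blood pressure variability (BPV) compared to daytime". That sentence concerns nighttime variability, not the dipping class; Methods calls the patterns only relevant to prognosis. A reader might also infer that the class test halves the power. The documents contain no figure for dipping from which that could follow. It fits assumed effects of about 0.5-0.8 SD and overstates the loss at larger ones.

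**Conclusion.** The point holds in a limited form. The overlap between dipper and non-dipper is certain from the text and prevents a unique table. The unordered four-class comparison is the natural reading of the plan, not a stated one. If it is carried out, it loses power against a test of the continuous fall in every non-null scenario tried. The loss against Mann-Whitney is roughly a quarter to somewhat over half for effects of 0.5 to 1.15 SD, and falls to 16-22% at 1.4 SD with 15 per arm. These sizes rest wholly on assumed means, SDs, normality and a pure shift; the ANCOVA figures also rest on an assumed correlation of 0.4.

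It does not follow that the trial is bound to miss a sizeable change in dipping: at a 7-point shift with 15 per arm the class test still has about 46-61% power. Nor does the point touch the main comparison, because the trial was sized on SBP and DBP. It is a worthwhile improvement to an additional outcome.

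**What to change.** In the Analysis section, prespecify the percentage nocturnal fall, (day mean - night mean)/day mean × 100, for SBP and separately for DBP, as a continuous outcome. Compare the arms at the final visit with adjustment for the baseline fall, and give the difference with a 95% CI.

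If the non-parametric framework is kept, name Mann-Whitney on the change in fall from baseline. The Mann-Whitney power shown above is for the final value; with a correlation below 0.5 the change is noisier, so adjustment is the better choice.

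In Methods, reconcile the dipper and non-dipper boundaries so that each patient falls in exactly one class, and state which pressure defines the class. This is needed even for a descriptive table. Then report the classes as counts and baseline-to-final shifts, without a test.

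The cost is wording only, since day and night BP are already recorded. The small downside is that there is no p-value for the dipping classes.
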